9.6.1.2.1 VO₂max

For VO₂max recorded values and the changes from baseline will be listed and summarized. For each visit within each study arm VO₂max (observed values, weight-adjusted- and fat free weight-adjusted values) will be summarized by sex and cigarette consumption at V1. Both acute and training baseline will be presented for VO2_{max}.

Box plots will be prepared for VO_2max changes from baseline presenting the study arms side by side separately for each visit.

9.6.1.2.2 Exercise capacity

For exercise capacity recorded values and the changes from baseline will be listed and summarized. For each visit within each study arm exercise capacity will in addition be summarized by sex and cigarette consumption at V1. Both acute and training baseline will be presented for exercise capacity.

Box plots will be prepared for changes in exercise capacity from baseline presenting the study arms side by side separately for each visit.

9.6.1.2.3 Intensity of exercise training

For the intensity of the exercise training recorded values will be listed. The following variables will be summarized at V5 (baseline), V14, V29 and V41 so that all subjects are on training program 1.

Confidentiality Statement

Philip Morris Products SA.	Statistical Analysis Plan	Confidential
P1-EXC-01-EU	Final 2.0	Page 49 of 71
Related to PMI-RRP-WKI-112487		

- Cumulative work produced during each training session (calories and calories/kg body weight)
- Average work rate during each training session (watt and watt/kg body weight)
- Average heart rate (HR) during each training session (bpm)

For cumulative work and average work rate they will be plotted for V5, V14, V29 and V41 using box plots with the response on the y-axis and month on the x-axis, within each month there will be a box plot for each product use category. Average heart rate will only be summarized and not plotted as the exercises are controlled for heart rate.

- Time spent at 0-50%, 50-65%, 65-75%, 75-90%, >90% of maximal work rate during each training session (sec)
- Time spent at 0-50%, 50-65%, 65-75%, 75-90%, >90% of maximal HR during each training session (sec).

For the time spent at maximum work rate or heart rate the data will again be summarized at only visits V5, V14, V29 and V41. Time spent at the various intervals of maximal work rate will be plotted using stacked bars for each product use group at each visit. Time spent in an interval of maximal heart rate will not be plotted.

Within each study arm the following variables will be summarized by interval (0-5, 6-20, 21-30, and 31-40 minutes) at V5, V14, V29 and V41.

- Intensity (%) {percent of maximal workload}
- Work rate (watt)
- Work rate per body weight (watt/kg body weight).

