#### Endpoint (V3, V4 and V43)

- VO2max as determined during maximal cycle ergometer exercise (expressed in absolute [mL\*min], weight-adjusted [mL\*kg\*min] and fat free weight-adjusted [mL\*kg\*min] values)
  - 2. To evaluate changes in exercise capacity in subjects switching to *IQOS* (with and without training), continuing to smoke cigarettes (with training) and being smoking abstinent (with training)

Endpoints (V3, V4 and V43)

- Exercise capacity: time to complete a pre-defined work on a cycle ergometer (min:sec)
  - 3. To assess the intensity of the exercise training in subjects participating in a training program and switching to *IQOS*, continuing to smoke cigarettes and being smoking abstinent

Endpoints (V5-V42)

- Cumulative work produced during each training session (calories and calories/kg body weight)
- Average work rate during each training session (watt and watt/kg body weight)
- Average work rate during each interval during each training session (watt and watt/kg body weight)
- Time spent at 0-50%, 50-65%, 65-75%, 75-90%, >90% of maximal work rate during each training session (min:sec)
- Average heart rate (HR) during each training session (bpm)
- Time spent at 0-50%, 50-60%, 60-70%, 70-80 % and >80 % of maximal HR during each training session (min:sec)

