### **Confidentiality Statement**

Philip Morris Products SA	Clinical Study Protocol	Confidential
P1-EXC-01-EU	Version 3.0 / 2 May 2019	Page 105 of 151

cigarette consumption and/or *IQOS* may also be used as a covariate. Further details will be provided in the SAP.

Estimates of variability from the statistical model will be reported and may be used to power future similar studies.

Descriptive statistics will be used to present various measures assessing the intensity of exercise training in each arm. This includes the cumulative work produced (calories and calories/kg body weight), average work rate during each training session (watt and watt/kg body weight), average work rate during each interval during each training session (watt and watt/kg body weight), time spent at 0-50%, 50-65%, 65-75%, 75-90%, >90% of maximal work rate during each training session (min:sec), average heart rate (HR) during each training session (bpm) and time spent at 0-50%, 50-60%, 60-70%, 70-80 % and >80 % of maximal HR during each training session (min:sec).

To evaluate changes in physiological parameters and perception of exertion and capacity in subjects switching to *IQOS*, continuing to smoke cigarettes and being smoking abstinent

An appropriate statistical model will be used to estimate the differences in physiological parameters and perception of exertion and capacity whilst adjusting for covariates such as age, sex, cigarette consumption and/or *IQOS* use or any other clinically relevant covariates of interest. The difference between arms (*IQOS*-1/SA vs cigarette) will be estimated and reported together with its 95% confidence intervals. All other pairwise comparisons between arms will be estimated and reported as well.

To monitor trends of daily physical activity levels during the study in subjects switching to *IQOS*, continuing to smoke cigarettes and being smoking abstinent

Descriptive statistics of the various measures of physical activity as measured by the mHealth wearable device will be reported. An appropriate statistical (linear or non-linear) model will be used to estimate the levels of activity taking into account clinically relevant covariates such as sex, cigarette consumption and age, and repeated measures over time. Estimates for each arm and all pairwise comparisons between arms will be reported using an appropriate statistical model as defined in the SAP.

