3 STUDY OBJECTIVES AND ENDPOINTS

3.1 Objectives and Endpoints

1. To evaluate changes in VO₂max in subjects switching to IQOS (with and without training), continuing to smoke cigarettes (with training) and being smoking abstinent (with training)

Endpoint (V3, V4 and V43)

- VO₂max as determined during maximal cycle ergometer exercise (expressed in absolute [mL*min⁻¹], weight-adjusted [mL*kg⁻¹*min⁻¹] and fat free weight-adjusted [mL*kg⁻¹*min⁻¹] values)
- 2. To evaluate changes in exercise capacity in subjects switching to IQOS (with and without training), continuing to smoke cigarettes (with training) and being smoking abstinent (with training)

Confidentiality Statement

Data and information contained in this document are considered to constitute trade secrets and confidential commercial information, and the legal protections provided to such trade secrets and confidential information are hereby claimed under the provisions of applicable law. No part of this document may be publicly disclosed without the written consent of Philip Morris Products S.A

Philip Morris Products SA.	Statistical Analysis Plan	Confidential
P1-EXC-01-EU	Final 2.0	Page 9 of 71
Related to PMI-RRP-WKI-112487		

Endpoints (V3, V4 and V43)

- Exercise capacity: time to complete a pre-defined work on a cycle ergometer (min:sec)
- 3. To assess the intensity of the exercise training in subjects participating in a training program and switching to IQOS, continuing to smoke cigarettes and being smoking abstinent

Endpoints (V5-V42)

- Cumulative work produced during each training session (calories and calories/kg body weight)
- Average work rate during each training session (watt and watt/kg body weight)
- Average work rate during each interval during each training session (watt and watt/kg body weight)
- Time spent at 0-50%, 50-65%, 65-75%, 75-90%, >90% of maximal work rate during each training session (min:sec)
- Average heart rate (HR) during each training session (bpm)
- Time spent at 0-50%, 50-60%, 60-70%, 70-80 % and >80 % of maximal HR during each training session (min:sec)
- 4. To evaluate changes in physiological parameters and perception of exertion and capacity in subjects switching to IQOS (with and without training), continuing to smoke cigarettes (with training) and being smoking abstinent (with training) Endpoints (V3, V43)

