6 SAMPLE SIZE JUSTIFICATION

The sample size of 20 per arm (smoking abstinence with training, IQOS with training, continued cigarette smoking with training) was determined based on previously published results, which reported a standard deviation of 14 mL/kg/min in VO₂max in the change

Confidentiality Statement

Philip Morris Products SA.	Statistical Analysis Plan	Confidential
P1-EXC-01-EU	Final 2.0	Page 30 of 71
Related to PMI-RRP-WKI-112487		SAD DI EYC OI EU

between groups which continued smoking and those who were smoking abstinent after participating in a 12-week training program (Albrecht, et al. 1998). This sample size allows a probability of 90% that the half-width of the 95% confidence intervals between two arms have a precision of approximately 10.3 mL/kg/min.

For example, if the mean difference in change between the cigarette arm and smoking abstinence arm was 12 mL/kg/min after training, we expect that if the experiment were repeated many times then on average 90% of the time the 95% confidence intervals of the mean differences between two arms will be within 1.7 and 22.3. To allow for a dropout rate of approximately 20%, the sample size will be 25 per arm. The IQOS-2 arm without training will mainly serve as a secondary analysis to the IQOS-1 arm with training, and the drop-out rate in this arm is expected to be lower. Therefore, only 15 subjects will be randomized to this arm.

CHANGES FROM THE PROTOCOL SPECIFIED STATISTICAL 7 ANALYSES

An exploratory analysis of VO2max and exercise capacity will be carried out on subjects with additional biochemical verification of smoking status.

8 **ANALYSIS SETS**

The main population for non-safety analysis will be the As Exposed Exercise Compliant Set. Safety will be analyzed using the Safety Set.

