Estimates of the endpoints at V14, V28, V42 (corresponding to the end of the 1st, 2nd and 3rd month of training) and their 95% confidence intervals will be presented as per the comparisons listed in Table 5 except for IQOS-2 and Dual-2 groups as they did not participate in any exercise training. Estimates of study arms and pairwise comparisons of study arms will be tabulated over all visits as well as separately for each visit.

An example of SAS code for the model to be used is provided below:

```
proc mixed data= _DATA_ method=reml order=data;
class SUBJECT VISIT ARM SEX CC_CONS_GRP;
model ENDPOINT = ARM SEX AGE CC_CONS_GRP DAILY_CC_USE VISIT VISIT*ARM
/ddfm = kr;
random SUBJECT / subject = SUBJECT;
repeated VISIT / type=ar(1) subject = SUBJECT;
lsmeans ARM / diff=control("CC") CL alpha=0.05 bylevel e;
lsmeans ARM / diff=control("IQOS-1") CL alpha=0.05 bylevel e;
lsmeans VISIT*ARM / diff=control("VISIT#X" "CC") CL alpha=0.05 bylevel e;
```

Confidentiality Statement

Philip Morris Products SA.	Statistical Analysis Plan	Confidential
P1-EXC-01-EU	Final 2.0	Page 43 of 71
Related to PMI-RRP-WKI-112487		SAP P1-EXC-01-EU

```
lsmeans VISIT*ARM / diff=control("VISIT#X" "IQOS-1") CL alpha=0.05 bylevel
e;
run;
```

Estimates of variability (e.g. "Covariance Parameter Estimates") from the statistical model will be reported (at least in the original statistical output listings) and may be used to power future similar studies.

The average work rate during each interval at each training session, average heart rate during each training session, time spent at various percentages of maximal work rate and time spent at various percentages of maximal heart rate will be summarized using only descriptive statistics. For the time spent at maximal work rate or heart rate the data will be summarized at V5, V14, V29 and V41 as subjects will be on training program 1 at these visits.

9.6.1.1.4 To evaluate changes in physiological parameters and perception of exertion and capacity in subjects switching to IQOS, continuing to smoke cigarettes and being smoking abstinent

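### SAP 9.6.1.2.3 tabulates time in heart-rate bands that differ, without a declared change, from the endpoint in SAP 3.1 and protocol 3.1 and 12.5

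*SAP*

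**What the plan says.** Objective 3 has two separate time-in-band endpoints, with different cut-points.

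- **Heart rate.** Protocol 12.5, which describes the planned analysis, has "time spent at 0-50%, 50-60%, 60-70%, 70-80 % and >80 % of maximal HR during each training session (min:sec". The protocol synopsis and protocol 3.1 give the same bands. SAP 3.1 repeats them: "Time spent at 0-50%, 50-60%, 60-70%, 70-80 % and >80 % of maximal HR during each training session (min:sec".
- **Work rate.** Protocol 3.1 has "Time spent at 0-50%, 50-65%, 65-75%, 75-90%, >90% of maximal work rate during each training session (min:sec".

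SAP 9.6.1.2.3 specifies the summaries. Its work-rate bullet keeps the protocol bands: "Time spent at 0-50%, 50-65%, 65-75%, 75-90%, >90% of maximal work rate during each training session (sec". The heart-rate bullet that follows does not: "Time spent at 0-50%, 50-65%, 65-75%, 75-90%, >90% of maximal HR during each training session (sec".

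Nothing else in the SAP analysis text sets cut-points for heart rate. SAP 9.6.1.1.3 says only that "time spent at various percentages of maximal heart rate will be summarized using only descriptive statistics". SAP 9.6.1.2.3 adds: "Time spent in an interval of maximal heart rate will not be plotted". The table titles in SAP 13.2 name no bands.

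SAP section 7, on changes from the protocol analyses, contains a single item: "An exploratory analysis of VO2max and exercise capacity will be carried out on subjects with additional biochemical verification of smoking status". The revision history in SAP 1.1 does not mention heart-rate bands.

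**The concern.** The SAP gives two definitions of one endpoint, and a programmer cannot satisfy both. The only analysis text with cut-points carries the version that departs from the protocol. If it is followed, the study report would contain a heart-rate table that does not match the endpoint stated in the objectives of either document, and nothing would tell the reader why.

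The endpoint describes how hard subjects actually trained. SAP 9.1.4 gives it a data-quality rule of its own: sessions with less than 80% of the heart-rate recording are left out. A table cut at other points would answer a somewhat different question about the same sessions.

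**Working it through.** **Step 1: set the cut-points side by side** (percentage of the maximum).

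| Source | Quantity | Inner cut-points |
|---|---|---|
| Protocol synopsis, 3.1 and 12.5 | Heart rate | 50, 60, 70, 80 |
| SAP 3.1 | Heart rate | 50, 60, 70, 80 |
| SAP 9.6.1.2.3 | Heart rate | 50, 65, 75, 90 |
| Protocol 3.1; SAP 3.1 and 9.6.1.2.3 | Work rate | 50, 65, 75, 90 |

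The heart-rate cuts in SAP 9.6.1.2.3 equal the work-rate cuts and differ from every other statement of the heart-rate bands. The change of unit from min:sec to seconds is not part of the problem, because SAP 9.1.3 announces it for both time-in-band endpoints.

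**Step 2: can the defined bands be rebuilt from the SAP table?** A band can be recovered by adding table cells only if both of its edges are table cut-points, here 0, 50, 65, 75, 90 or 100.

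| Defined band | Edges in the table? | Recoverable |
|---|---|---|
| 0-50% | 0 yes, 50 yes | Yes |
| 50-60% | 50 yes, 60 no | No |
| 60-70% | 60 no, 70 no | No |
| 70-80% | 70 no, 80 no | No |
| Above 80% | 80 no, 100 yes | No |

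One band of five is recoverable and four are not.

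**Step 3: does the difference lie where training takes place? (illustration only)** Protocol 7.6.3 sets training intensity at 60-85% and defines target heart rate as (HRmax − HRrest) × intensity + HRrest. Dividing by HRmax gives the target as a fraction of maximal heart rate:

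intensity + (1 − intensity) × HRrest/HRmax

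The documents give no resting or maximal heart rates. The values below are **assumptions**: resting 60-80 bpm and maximal 160-190 bpm.

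| HRrest / HRmax (assumed) | Lower target, intensity 0.60 | Upper target, intensity 0.85 |
|---|---|---|
| 60 / 190 | 0.60 + 0.40 × 0.316 = 72.6% | 0.85 + 0.15 × 0.316 = 89.7% |
| 70 / 175 | 0.60 + 0.40 × 0.400 = 76.0% | 0.85 + 0.15 × 0.400 = 91.0% |
| 80 / 160 | 0.60 + 0.40 × 0.500 = 80.0% | 0.85 + 0.15 × 0.500 = 92.5% |

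The first and last rows are the extremes of the assumed range. The lower target therefore runs from 72.6 to 80.0% of maximal heart rate, and the upper target from 89.7 to 92.5%.

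Under the defined bands, this region is divided once, at 80%. Under the bands in SAP 9.6.1.2.3, it is divided at 75% and 90%. The lower target falls below 75% when HRrest/HRmax is under 0.375 (0.60 + 0.40 × 0.375 = 0.75). The upper target exceeds 90% when the ratio is over one third (0.85 + 0.15/3 = 0.90). The same session can therefore be described differently by the two tables.

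This locates the target range. It does not give minutes per band, which depend on the length and intensity of each interval. Protocol Appendix 2 leaves those to a separate training manual.

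**The case against.** The mismatch itself is hard to dispute, but much can be said against making a lot of it.

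- **The endpoint does not vanish.** A reader might infer that time in heart-rate bands would go unreported. The documents do not support that. It would still be summarised, with other cut-points; the 0-50% band is unchanged; average heart rate per session is summarised; and recorded training values are listed. This stands.
- **A copying slip is not shown.** Because the two bullets carry the same numbers, a reader might conclude that the work-rate bands were pasted into the heart-rate line. That is plausible, but deliberate alignment of the two splits would leave the same text. The documents show identical bands and no reason for them. This stands too.
- **The table shells may be right.** SAP section 1 puts the detailed table layouts in a separate document that is not available here, and SAP 3.1 still has the protocol bands, so the final table could follow either. This softens the prediction. It does not remove the contradiction within the SAP.
- **No shift of training time can be claimed.** A reader might conclude that most session minutes would move into particular bands. The heart rates in the illustration are assumed and the interval lengths are not available, so no such split can be derived.
- **Little depends on it.** The endpoint is descriptive and not plotted, sessions are controlled for heart rate, and the study tests no hypothesis. This is right, and it limits the importance of the point.

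**Conclusion.** The inconsistency is real and undeclared. SAP 9.6.1.2.3 contradicts SAP 3.1 and protocol 3.1 and 12.5, and if it is followed, four of the five defined heart-rate bands would be neither summarised nor recoverable from the table. That conclusion rests only on the printed cut-points and needs no assumption.

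The statement that the difference falls in the training range rests on the assumed heart rates and is illustrative. The point supports no claim that heart-rate time would go unreported, and none about bias between arms.

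The consequence is small: one descriptive endpoint at four visits (V5, V14, V29 and V41). The VO2max and exercise-capacity estimates, the sample size and the safety results are unaffected. It is worth correcting because the correction is simple.

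**What to change.** In SAP 9.6.1.2.3, replace the heart-rate bands with those of SAP 3.1 and protocol 3.1 and 12.5: 0-50, 50-60, 60-70, 70-80 and above 80% of maximal heart rate. The bands now printed there may stay as a supplementary split, labelled as such.

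If the new bands were intended, keep them, give the reason in SAP section 7 as a departure from the protocol, and align SAP 3.1.

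In either case, check that the table shells use the same bands. The cost is one line of the SAP for the first option and a short entry in two sections for the second. No new data are needed. It is best settled before the tables are programmed.

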9.6.1.2.4 Physiological parameters and perception of exertion and capacity

For blood composition recorded values and derived (or computed) values as well as the changes from baseline will be listed and commonly summarized by arm. Derived endpoints (Hbmass, RBCV, BV, and PV) are described in Section 5.2 "Blood composition as determined by CO re-breathing method". Lactate values (continuous) and Borg RPE scale values (categorical) will be listed; they will be summarized within each study arm (and overall) for each visit at rest and at each 25 Watt workload increase.

For the BORG scale, a mosaic plot showing the number of subjects with BORG scale > 16 and the number of subjects with BORG scale < 16 (y-axis) versus maximum wattage during the VO2max test (x-axis) will be plotted separately for each study arm.

Respiratory parameters (continuous) with changes from baseline and Rating of Perceived Capacity (RPC) scale values (categorical) will be listed and summarized. Both acute and

Data and information contained in this document are considered to constitute trade secrets and confidential commercial information, and the legal protections provided to such trade secrets and confidential information are hereby claimed under the provisions of applicable law. No part of this document may be publicly disclosed without the written consent of Philip Morris Products S.A

Philip Morris Products SA.	Statistical Analysis Plan	Confidential
P1-EXC-01-EU	Final 2.0	Page 50 of 71
Related to PMI-RRP-WKI-112487		CAD DI EVC AL EU

training baseline will be presented for these parameters as well. Although the RPC is a categorical (actually ordinal) scale it will be summarized as a continuous variable by visit, arm and stratified by sex. Scatter plots of the RPC scale vs the corresponding VO₂max value at each visit will be plotted.

Heart rate and oxygen uptake (VO_2) will be listed; these data will be summarized within each study arm for each visit at rest and at each 25 Watt workload increase.

9.6.1.2.5 Daily physical activity

For step count raw values will be averaged and reported by month. Measures of physical activity and changes from baseline will be listed and summarized by visit and actual product use for baseline and each month.

9.6.1.2.6 Biological health markers

For biological health markers the changes from baseline for each arm as endpoint, therefore the observed values and the changes from baseline will be listed and summarized by visit and arm.

9.6.1.2.7 Weight, body fat and waist circumference

For body fat and waist circumference (V3, V4 and V43) both the observed values and the changes from baseline will be listed and summarized by visit and arm. For weight (V3-V43) the data will be summarized for each month (see section 9.1.3.1) by visit and arm.

9.6.1.2.8 Exposure to CO, nicotine, nitrosamines and acrylonitrile

For exhaled CO and COHb% in blood both the observed values and the changes from baseline will be listed and summarized at Baseline, V4 and by month (see section 9.1.3.1) for each arm. The reporting of COHb% will on the log-scale then back-transformed to obtain the geometric means.

For NEQ, NNAL and CEMA in urine the values adjusted for creatinine will be listed. For the latter also the changes from baseline will be listed. The values adjusted for creatinine and their changes from baseline will be summarized by visit and arm. Similar to COHb%, these values will be log-transformed and means calculated, these values are then back transformed to obtain the geometric means.

Data and information contained in this document are considered to constitute trade secrets and confidential commercial information, and the legal protections provided to such trade secrets and confidential information are hereby claimed under the provisions of applicable law. No part of this document may be publicly disclosed without the written consent of Philip Morris Products S.A

Philip Morris Products SA.	Statistical Analysis Plan	Confidential
P1-EXC-01-EU	Final 2.0	Page 51 of 71
Related to PMI-RRP-WKI-112487		

